### 10.2.4 Duration of Treatment

Patients of all three dose groups will receive treatment with CLS12311 within 13 weeks from enrollment in the study. CLS12311 will be administered at [REDACTED] for sentinel patients and at [REDACTED] for all other patients. CLS12311 will be manufactured from blood donations taken in [REDACTED] for treatments in [REDACTED] and from blood donation taken in [REDACTED] for treatments given [REDACTED]. Due to organizational reasons, the study design and the manufacturing schedule, the treatments may be postponed. However, both treatments of one cycle will be administered with an [REDACTED]. The sponsor and the manufacturer of the IMP will closely coordinate with the sites and other involved parties to organize all respective study visits, ensuring the adherence to the protocol. A minimum interval of [REDACTED] between the two blood donations will be maintained.

### 10.3 Labelling

The labels for CLS12311/placebo and protective containers will be designed in accordance with GMP annex 13 and relevant regulatory requirements, including CTR and applicable national regulations. At a minimum, the study treatment label will include a study reference code, drug identifier, patient identifier, lot number, expiry or use-by date and time. In addition, the patient's name (surname, first name) and date of birth will be listed on the label in order to comply with transfusion medicine regulations for autologous red blood cell products.

### 10.4 Packaging

CLS12311/ placebo is manufactured by TETEC AG and is supplied as a sterile liquid drug product for i.v. administration. It is provided in blood bags, each containing 150 ml CLS12311 or placebo.

The IMP/ placebo is shipped to the sites in temperature-controlled cooling boxes, designed to keep the product at 2-10°C during transport.

To ensure the integrity of the product, each shipment will include a temperature monitoring device to verify that the product remained within the required temperature range throughout the transport process.

### 10.5 Storage

Upon arrival at the site, the IMP/placebo must be stored in a temperature-controlled fridge at 2-8°C, if not directly administered. The IMP/placebo must be kept restricted to authorized personnel, and the product must be stored in a secure, locked area to prevent unauthorized access. Correct storage is essential for the IMPs to retain their safety and potency for the duration of their assigned shelf life.

Detailed instructions on the storage conditions and handling procedures are provided in the Logistics Manual, including requirements for temperature monitoring and documentation of any deviations.

Strict adherence to the storage requirements will be monitored through regular site monitoring and temperature log reviews.

### 10.6 Investigational Medicinal Product Accountability

The IMPs required for completion of this study (CLS12311 [or placebo] will be provided by the Sponsor. The study site (i.e. investigator or other authorized personnel e.g. pharmacist) is responsible for maintaining records of IMP delivery to the site, IMP use in each patient, and disposition of any unused IMP. This ensures reconciliation of all IMPs received and guarantees that patients are provided with doses as specified by the protocol.

The study site should follow all instructions included with each IMP shipment. The investigator or authorized designee must confirm that appropriate temperature conditions have been maintained during transit for all IMPs received and that any discrepancies have been reported and resolved before use of the IMPs. All IMPs must be stored in a secure and monitored (manual or automated) area in accordance with the labelled storage conditions, with access limited to the investigator and authorized staff. Further details are described in the Logistics Manual.

Only patients enrolled in the study may receive IMPs, and only authorized staff may administer IMPs. Accurate records of all IMPs received, dispensed and disposed of at the study site should be recorded on the Drug Accountability Form.

These Drug Accountability Forms should include dates and time of administration, dose completeness (complete or incomplete dose), batch numbers, expiration dates, and the unique code numbers assigned to study patients.

Monitoring of drug accountability will be performed by the field monitor during site visits and at the completion of the trial.

Copies of the completed Drug Accountability Forms must be retained in the Investigator's Site Files (ISF), and the document must be filed in the Sponsor Trial Master File (TMF) at the latest after the completion of the study.

### 10.7 Destruction / Retrieval of Surplus Investigational Medicinal Products

Unused or surplus IMP/Placebo will be disposed of at the study site as medical waste in conformity with national regulations. The destruction has to be recorded accordingly on the study specific destruction form.

## 11 CONCOMITANT THERAPY

A concomitant medication is any treatment (e.g. prescription drugs, over-the-counter drugs, vaccines, herbal or homeopathic remedies, nutritional supplements) received by the patient during the study aside from the IMP/placebo.

Concomitant medications should be kept to a minimum during the study. However, if these are considered necessary for the patient's welfare and are unlikely to interfere with the IMP, they may be given at the discretion of the Investigator or Study Physician and must be recorded in the eCRF.

Symptomatic therapies such as treatments for spasticity, bladder dysfunction, depression, or fatigue are not restricted, but should be optimized as early as possible during baseline and pre-treatment in an attempt to maintain consistent treatment for the duration of the study.

Patients who use oral contraceptives or hormone-replacement therapy should continue their use.

### 11.1 Therapies not allowed during the Study

Any of the drugs mentioned under Exclusion Criterion No. 2 (see Section 8.1.2) will not be allowed during the study.

Patients may not receive systemic corticosteroid therapy except for the treatment of relapses (see section 11.2).

Patients may not receive any other investigational product including investigational symptomatic therapies for MS and investigational therapies for non-MS indications.

In the Safety Follow Up period there are no restrictions regarding concomitant medication.

### 11.2 Standardized Acute Therapy for Relapses during the Study

Relapses are to be treated with standard i.v. corticosteroids if clinically necessary according to the Investigator's judgement. The standard treatment regimen is i.v. methylprednisolone 1g, daily for 3-5 days. If required a second cycle may be given.

#### Impact of corticosteroid treatment on scheduled MRIs:

MRIs will be performed as per schedule irrespective of corticosteroid treatment.

#### Impact of corticosteroid treatment on blood donation and study drug administration:

If relapse treatment is started prior to blood donation or IMP administration the visit shall be postponed until the end of corticosteroid therapy, i.e. the visit can be performed the day after the last corticosteroid dose at the earliest.

Use of steroid treatment must be recorded on the concomitant medications eCRF.

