- if at least 3 patients experience AEs graded as 'moderate' and at least possibly related to the IMP within the same dose level of CLS12311/placebo
- If at least 3 patients (irrespective of the dose group) show an increase of >5 new lesions (CEL or new/enlarging T2) at [REDACTED] compared to the average number of new brain lesions (as defined above) observed during baseline
- if a confirmed relapse (irrespective of the dose group), assessed as severe, occurred within 4 weeks after the last dosing

The DSMB shall give recommendations on the following main outcomes:

- stop further treatment or lower further dosing in individual patients
- stop recruitment and/or treatment or lower dose for a specific treatment arm
- stop recruitment and/or treatment for the clinical trial
- continue the clinical trial as per protocol
- any other trial modification (e.g. additional visits, assessments)

Any recommendation will be explicitly documented in the meeting minutes.

Based on the DSMB recommendations, the Study Steering Committee will decide on actions to be taken as outlined above.

For the DSMB meetings, the DSMB will receive patient listings and statistical summaries, consisting of at least the following in addition to all available data on the patient(s) that made the meeting necessary:

- All patients who experienced SAEs (including relationship and severity)
- All patients who experienced AEs (including relationship and severity)
- All patients who experienced AEs within one day following infusion of CLS12311/placebo including severity and relationship
- All patients who experienced a relapse
- Number of new brain lesions (CEL and new/enlarging T2)
- EDSS scores
- Safety relevant protocol deviations

Detailed requirements on the presentation of listings and summaries and details of the premise and the scope of the DSMB will be specified in the DSMB Charter.

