### 7.1 Open Label Treatment Phase: at least 17 weeks

The key measures, which have been implemented to ensure the safety of trial participants are briefly highlighted:

- Single ascending dosing starting with sentinel patient in each dose group
- An interval of at least 4 days between dosing of patients
- Safety assessments between dosing of each patient
- A scheduled DSMB meeting to assess safety of dosing after the last patient completes [REDACTED]
- Stringent criteria have been defined to trigger immediate DSMB safety assessments at any time during the trial
- Strict enrollment to allow safety assessment of the first treatment cycle prior to administration of second treatment cycle
- The second treatment cycle to be administered only after the safety of the first treatment cycle of the higher dose group has been confirmed
- The cumulative dose during second treatment cycle does not exceed the total dose of the first treatment cycle, for which safety had already been confirmed

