#### 12.1.1.2 MS Relapse

MS relapse definition: appearance of a new neurological abnormality or worsening of previously stable or improving pre-existing neurological abnormality, separated by at least 30 days from onset of a preceding clinical relapse-qualifying event [5]. The abnormality must have been present for at least 24 hours and occurred in the absence of fever ( $< 37.5^{\circ}\text{C}$ ) or known infection.

Severe relapses involve 1) at least one of the following functional systems: motor, cerebellar, brainstem, spinal cord and 2) lead to an increase in EDSS of at least 1 point. A patient may report symptoms indicative of a relapse at a scheduled visit or at any other time.

Patients will be instructed to contact the Investigator if he/she develops new or reoccurring or worsening neurological signs/symptoms indicative of relapse. At each scheduled visit, the patient will also be asked whether such symptoms have occurred. If a patient reports new neurological symptoms or worsening of previous symptoms, a relapse assessment will be performed and sent for confirmation to the Medical Monitor.

Reporting of relapse: MS relapses should not be recorded as adverse events. However, MS relapses will be recorded on a separate relapse form in the eCRF. In addition, all relapses reported by the Investigators in the eCRF will be reviewed individually on an ongoing basis by an expert neurologist to decide whether the event qualifies for a true relapse in the context of this study (see definition above).

Occasional isolated symptoms that according to the Investigator are caused by MS, but do not constitute a full MS relapse, should be reported as an adverse event.

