#### 14.5 Special Warnings and Precautionary Measures

**Allergic/anaphylactic and other infusion-related reactions:** As a precautionary measure, patients must be kept under medical supervision for at least 2 hours following IMP/placebo administration during the first treatment cycle to allow for an adequate observation and adequate treatment in case of potential allergic or other infusion related reactions. During the second treatment cycle the observation period is 1h following IMP administration. Furthermore, during the first treatment cycle, a telephone-based assessment of AEs will be done the day after IMP/placebo administration. In case of severe allergic (anaphylactic) reactions, standardized medical treatment should be applied. An example for an emergency treatment is given in the Appendix 24.2.

**Infection:** Some biologic and non-biologic therapies for the treatment of MS have been associated with an increased risk of infection. As a measure of precaution, the Investigator or Study Physicians are required to carefully monitor for any signs or symptoms of infection such as, but not limited to, increased body temperature, malaise, sweats, cough, dyspnea etc.

A **Data and Safety Monitoring Board (DSMB)** has been established to assess safety of patients treated in the study (for details on DSMB responsibilities see section 19.1.3).

**Investigators** are instructed not to proceed with the next IMP infusion if:

- the study participant is pregnant
- the study participant experienced allergic reaction in prior IMP administration
- the study participant experienced a severe infusion-related reaction in prior IMP administration
- the study participant experienced a serious AR to prior IMP administration
- the study participant experiences an SAE at the time of IMP infusion or any other serious medical condition, which poses a threat to the safety of IMP administration
- the Sponsor or Steering Committee or DSMB have decided to not continue IMP administration in the trial arm concerned

In case of questions or uncertainties regarding IMP administration following adverse events, the Investigator should contact the medical monitor (primary contact) or the Sponsor's Medical Representative. Contact details are given at the beginning of the study protocol.

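### A confirmed severe relapse within 4 weeks after dosing requires a DSMB meeting, but no protocol text automatically holds that patient's next infusion while the meeting is pending

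*Protocol*

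**What the plan says.** **The trigger.** The Synopsis (Data and Safety Monitoring) lists four criteria that require an extra DSMB meeting. One is "if a confirmed relapse (irrespective of the dose group), assessed as severe, occurred within 4 weeks after the last dosing". Section 7.1 presents the triggers as a key safety measure: "Stringent criteria have been defined to trigger immediate DSMB safety assessments at any time during the trial".

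**Timing of the next infusion after a relapse.** Section 11.2 leaves steroids to the investigator's judgement, with a standard course of 3-5 days and a second course if needed. If relapse treatment starts before a donation or infusion, the visit is postponed, and "the visit can be performed the day after the last corticosteroid dose at the earliest".

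**The do-not-proceed list.** Section 14.5 tells investigators not to give the next infusion in six situations. They include "the study participant experienced a severe infusion-related reaction in prior IMP administration", "the study participant experienced a serious AR to prior IMP administration", an SAE at the time of infusion or "any other serious medical condition, which poses a threat to the safety of IMP administration", and the case where "the Sponsor or Steering Committee or DSMB have decided to not continue IMP administration in the trial arm concerned". Pregnancy and a prior allergic reaction complete the list.

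**Status of relapses.** Section 12.1.1.2 states that "MS relapses should not be recorded as adverse events". They go on a separate form, to the Medical Monitor for confirmation and to an expert neurologist for review.

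**Withdrawal.** The Withdrawal Criteria in the Synopsis oblige withdrawal for a condition that physicians and investigators consider severe or compromising for the patient's safety or the study results.

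**The concern.** The protocol makes one severe relapse after dosing serious enough to convene the DSMB, but it attaches no interim consequence for the patient who had it. CLS12311 is first-in-human. Section 13.4.5 does not rule out that the product could provoke an immune response that worsens the disease, and relapse is part of the primary safety endpoint. Section 5.2.2 justifies splitting each cycle partly by the chance to assess safety before the next infusion, but it does not say that an open review stops that infusion.

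At stake is whether a patient could receive more peptide-coupled cells before the body asked to judge the relapse has met. On the text, that depends on someone judging the case serious enough in time. No rule takes effect by itself.

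**Working it through.** The plan gives no figure to reproduce here, so the check sets the rules side by side, with some counting.

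**1. Delay under 11.2.** Count the first steroid dose as day 1. The earliest infusion day is the number of steroid days + 1.
- One course: 3 + 1 = day 4, to 5 + 1 = day 6.
- Two courses back to back (assumption; 11.2 gives no gap): 6 + 1 = day 7, to 10 + 1 = day 11.
- No steroids: no delay required.

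None of these days is linked to adjudication or to the DSMB meeting. The protocol sets no deadline for either.

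**2. The six items in 14.5, applied to a confirmed severe relapse with the DSMB meeting pending.**

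| Item | Does it stop the infusion automatically? |
|---|---|
| Pregnancy | No, unrelated |
| Allergic reaction to prior IMP | No, unrelated |
| Severe infusion-related reaction | No, not a relapse |
| Serious AR to prior IMP | Not clearly: 13.1.6 defines an AR as a kind of AE, and relapses are not AEs (12.1.1.2, 13.1.1) |
| SAE, or other serious condition threatening safe administration | SAE part: not clearly, for the same reason. Other part: yes, once someone judges that it applies |
| Decision by Sponsor, Steering Committee or DSMB | Only once taken, and worded for a trial arm |

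Items that name relapse or a pending triggered review: 0 of 6.

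**3. Other stops.** The withdrawal criterion binds once the condition is deemed severe or compromising. Section 9.3.3 allows withdrawal at the investigator's or Sponsor's discretion. Section 19.7 lets the Sponsor act on an immediate hazard. Relapse is assessed at each infusion visit (14.1.3). The second-cycle gates in 7.1 rest mainly on other patients' data and do not cover the second infusion within a cycle. None of these is tied to the open DSMB review.

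**4. Where active re-exposure within a cycle can occur.** The Synopsis (Dosing) shows peptide-coupled cells on both dosing days in groups 2 and 3. In group 1, both bags on the second dosing day are placebo.
- Cycle 1, groups 2 and 3: 3 + 4 = 7 patients.
- Cycle 2, groups 2 and 3: 2 + 3 = 5 patients.
- Planned active second dosing days: 7 + 5 = 12. Placebo-only second dosing days in group 1: 2 + 1 = 3.

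**5. Is the gap between infusions inside the trigger window?** The window is 4 weeks, or 28 days. The one unredacted dosing week puts group 1's second day of cycle 1 at Week 3. Baseline is Week 0 and a donation comes before the first infusion, so the nominal gap there is under 21 days. For groups 2 and 3 the weeks are redacted. If their gap is 28 days or less (assumption), every severe relapse between the two infusions falls in the window; if it is longer, only those in the first 28 days do. How often this would happen cannot be computed.

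**The case against.** The strongest reply is that the protocol is not silent. A reader might infer that every available stop is merely discretionary. The documents do not support that. Withdrawal is obligatory for a condition deemed severe or compromising, 14.5 is worded as an instruction, and the steroid postponement is mandatory once steroids are given. What stands of the concern is narrower: apart from the steroid delay, each stop needs a judgement or decision first, and none refers to the pending review.

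A reader might also take 11.2 as clearance to dose the day after steroids end. It is a minimum delay on account of steroids and does not override 14.5 or the withdrawal criteria. It simply adds no hold for the relapse itself.

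The Week 3 interval might seem to show active re-exposure during an open review. It does not, because that infusion is placebo only.

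Nor is the relapse trigger clearly worse served than the trigger for a severe related AE. A severe related AE that is not serious, allergic or infusion-related has no named hold in 14.5 either.

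Finally, nine patients are dosed under central coordination, with at most one starting treatment per week, so sites do not schedule infusions on their own. Both documents leave DSMB details to a Charter. These points lower the likelihood of the problem, but they do not put a hold in the text that investigators follow.

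**Conclusion.** The point holds as a gap in the protocol text. A confirmed severe relapse within 4 weeks after dosing obliges the DSMB to meet, and nothing automatically holds that patient's next infusion until it has done so. The existing stops act only after someone has judged or decided.

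The gap is small in number but concerns the main mechanism-related risk: up to 12 planned second dosing days with active product, in seven patients of groups 2 and 3. Exposure in time depends on redacted intervals, so no frequency can be given. The conclusion is limited to the protocol and SAP; the DSMB Charter may already contain a hold. The documents do not show that any patient was re-dosed during a pending review, or that the protocol tells sites to do so.

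A separate clerical fault is that 13.4.5 sends the reader to 19.1.3 for the trigger rules, which 19.1.3 does not print.

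**What to change.** Add one item to the do-not-proceed list in 14.5, with a cross-reference in 11.2:

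> *the study participant had a relapse assessed as severe, or under adjudication for severity, within 4 weeks after the last dosing, until adjudication is complete and, if confirmed as severe, the DSMB recommendation has been acted on; if the product expires meanwhile, the infusion is omitted and the patient stays on study.*

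Also print the four DSMB triggers in 19.1.3. If the Charter already contains a hold, the 14.5 item should match it.

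The cost is wording in three sections and a delayed or lost infusion in the affected patient, since all bags of a cycle come from one donation. The omission rule must be explicit, because the stay-on-study rule in 13.4.6 is written for manufacturing, transport and compatibility failures. A lost infusion matters most in patients 3 and 6, whose data release repeat dosing in patients 2, 4 and 5. Section 9.3.1 already lets the Sponsor replace a patient with insufficient safety information.

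The SAP was finalised in February 2026 after data review, so dosing has probably ended. In that case the wording belongs in any later CLS12311 protocol.

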## 12 DEFINITION OF THE PRIMARY AND SECONDARY VARIABLES

### 12.1 Primary Variable(s)

#### 12.1.1 Safety Variables

The primary safety outcome is the number and severity of AEs and SAEs and/or worsening of disease measured by clinical (relapses) and imaging (number and size of brain lesions) parameters, following different doses of CLS12311.

##### 12.1.1.1 Adverse Events (AEs)

AEs might either be observed by the Investigator during scheduled clinical examinations (e.g. physical examination, AE assessment, see below) or during unscheduled clinical examinations

or reported by the patient. AEs will have to be documented throughout the trial as described in Section 13. Event description, start/stop dates, severity, relationship to treatment (i.e. blood donation, CLS12311 or placebo), outcome and seriousness (yes or no) will be recorded.

Of particular interest are the following classes of AEs:

- Treatment related AEs
- Treatment related SAEs
- AEs of special interest (AESIs) are AEs considered severe and related to the IMP occurring within one day (i.e. occurring on the treatment day or on the day after treatment) following infusion of CLS12311/placebo: dyspnea, tachycardia, fever, chills, malaise, shock, infection, allergic reaction, renal or liver failure.

